Tricyclic antidepressants (TCAs)	Angiotensin converting enzyme inhibitors (ACEi)
Typical antipsychotics	Calcium channel blockers
Anticoagulants	Beta blockers
Antiplatelet agents	

Comorbid conditions	
Atrial fibrillation	Chronic liver disease
Coronary artery disease	Asthma
Heart failure	Ischemic heart disease
Stroke or transient ischemic attack	Chronic obstructive pulmonary disease
Peripheral vascular disease	Malignancy
Hyperlipidemia	Drug or alcohol abuse or dependence
Renal dysfunction	Venous thromboembolism
Rheumatoid Arthritis	Hypertension

Other PAD treatments and PAD severity indicators	
Critical limb ischemia Thrombolytic therapy (streptokinase, urokinase, alteplase, tissue plasminogen activator (tPA), pro-urokinase, reteplase, tenecteplase and Staphylokinase)	Number of cardiologist visits Number of hospitalizations with PAD

ICD-9, ICD-10, HCPCS, and NDC codes used to define the covariates listed above are available in Appendix A.

c. Outcome variables and study follow-up:

- **Primary outcome:** incident dementia, i.e., Alzheimer's disease, vascular dementia, senile, presenile, or unspecified dementia, or dementia in other diseases classified elsewhere. Outcome will be defined by 1 inpatient

claim or 2 outpatient claims in analysis 1, 2, 3. In analysis 4, the outcome will be defined by 1 inpatient or 1 outpatient claims and 1 prescription claim for a symptomatic treatment [donepezil, galantamine, rivastigmine, and memantine] within 6 months of each other with outcome date assigned to second event in the sequence.

- Secondary outcomes: Individual component:

Alzheimer's disease

Condition	ICD-9 and ICD-10 codes
Alzheimer's disease	331.0*, F00*, G30*
Vascular dementia	290.4*, F01*
Senile, presenile, or unspecified dementia	290.0*, 290.1*. 290.3*, 797*, F03*
Dementia in other diseases classified elsewhere	331.1*, 331.2*, 331.7*, 294.1*, F02*

For analysis 1,3, and 4 the follow-up will start the day after initiation of Pentoxifylline and Cilostazol and will continue until the earliest date of the following events:

- The first occurrence of the outcome of interest
- The date of end of continuous registration in the database,
- End of the study period,
- Measured death event occurs,
- The date of drug discontinuation, defined as the date of the last continuous treatment episode of the index drug (Pentoxifylline and Cilostazol) plus a defined grace period (i.e., 90 days after the end of the last prescription's days' supply in main analyses).

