Other PAD treatments and PAD severity indicators , n (%)						
Critical limb ischemia	394 (23.2)	1058 (12.2)	0.29	381 (22.6)	380 (22.5)	0.00
Thrombolytic therapy	10 (0.6)	26 (0.3)	0.04	9 (0.5)	6 (0.4)	0.03
Number of cardiologist visits, mean (SD)	3.5 (5.9)	4 (5.2)	-0.08	3.5 (5.9)	3.5 (4.9)	-0.01
Number of hospitalizations with PAD, mean (SD)	0 (0.1)	0 (0.2)	-0.04	0 (0.1)	0 (0.1)	0.01
Comorbid conditions, n (%)						
Atrial fibrillation	296 (17.4)	1195 (13.7)	0.10	290 (17.2)	296 (17.5)	-0.01

DREAM study protocol - Comparison 12 Pentoxifylline vs Cilostazol

Chronic obstructive pulmonary disease	557 (32.7)	2821 (32.4)	0.01	550 (32.6)	556 (33)	-0.01
Chronic liver disease	91 (5.3)	591 (6.8)	-0.06	89 (5.3)	89 (5.3)	0.00
Drug or alcohol abuse or dependence	282 (16.6)	2134 (24.5)	-0.20	281 (16.7)	284 (16.8)	-0.01
Heart failure	336 (19.8)	1320 (15.2)	0.12	329 (19.5)	335 (19.9)	-0.01
Hyperlipidemia	1309 (77)	7176 (82.5)	-0.14	1300 (77.1)	1303 (77.2)	0.00
Ischemic heart disease	792 (46.6)	4714 (54.2)	-0.15	784 (46.5)	783 (46.4)	0.00
Malignancy	508 (29.9)	2426 (27.9)	0.04	502 (29.8)	517 (30.6)	-0.02
Peripheral vascular disease	1646 (96.8)	8451 (97.2)	-0.02	1634 (96.9)	1635 (96.9)	0.00
Rheumatoid Arthritis	112 (6.6)	348 (4)	0.12	108 (6.4)	100 (5.9)	0.02
Renal dysfunction	478 (28.1)	2178 (25)	0.07	471 (27.9)	478 (28.3)	-0.01
Stroke or transient ischemic attack	241 (14.2)	1170 (13.5)	0.02	236 (14)	242 (14.3)	-0.01
Venous thromboembolism	132 (7.8)	410 (4.7)	0.13	128 (7.6)	125 (7.4)	0.01

9. Statistical analysis plans

Incidence rates for the outcome will be estimated for the treatment and reference groups before and after PS matching. The competing risk of death could be of concern for the current set of analyses if mortality is frequent among patients included in the cohort and if differences in the risk of mortality between treatment and reference groups are substantial. In the PS-matched sample, we will use cause-specific hazard models⁸ to provide hazard ratios averaged over the entire follow-up period as well as interval specific hazard ratios (1, 2, and 3 years) for the association between the treatment of interest and risk of ADRD after considering all-cause mortality as a competing event. Pre-specified subgroup analyses will be conducted based on age, sex, and baseline cardiovascular disease.

10. References

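### Analysis 4 allows 6 months for the confirming record but ends follow-up 90 days after supply ends, so some dementia first recorded on treatment goes uncounted; a parallel version dated to the first record is needed

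*Combined protocol and SAP*

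**What the plan says.** Section 6c sets a two-record outcome for one analysis only: "In analysis 4, the outcome will be defined by 1 inpatient or 1 outpatient claims and 1 prescription claim for a symptomatic treatment". The two records must fall "within 6 months of each other with outcome date assigned to second event in the sequence".

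The same section gives analyses 1, 3 and 4 a common follow-up rule: "For analysis 1,3, and 4 the follow-up will start the day after initiation of Pentoxifylline and Cilostazol". Follow-up ends at the earliest of several events. One is "The first occurrence of the outcome of interest", which for analysis 4 means the date of the second record. Another is "The date of drug discontinuation, defined as the date of the last continuous treatment episode of the index drug", "plus a defined grace period (i.e., 90 days after the end of the last" prescription's days' supply. The 90 days is described as applying to the main analyses, and no other value is given for analysis 4.

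The available text does not let confirmation be sought after censoring, and it does not lengthen follow-up for analysis 4. Analysis 2 has no censoring at discontinuation, so the conflict does not arise there.

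Section 9 adds: "Incidence rates for the outcome will be estimated for the treatment and reference groups before and after PS matching".

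**The concern.** The confirmation window is about twice the grace period. Suppose the first dementia claim falls on the last day of supply and the symptomatic drug is filled 150 days later. The two records meet the 6-month definition, but follow-up ended on day 90. The patient contributes person-time and no event.

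Three things are at stake. First, events are lost from a comparison with only 1,687 matched pairs (section 8) and an outcome that already requires a prescription. Second, the arm-specific incidence rates promised in section 9 come to depend on how long patients stay on drug. Third, if a first dementia record leads to the PAD drug being stopped, the censoring is related to the outcome. The design diagrams in section 4 name informative censoring as something the set of analyses is meant to address.

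**Working it through.** The plan states no event count or loss figure for this point, so there is none to reproduce.

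**Inputs from section 6c.** Window: 6 months = 365.25/2 = 182.6 days. Grace period: 90 days.

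**Inputs not in the documents (assumed).** The gap between the two records, the length of treatment, the dementia rate, and whether a first record speeds stopping.

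**Step 1: which records are exposed.** Let R be the days from the first record to censoring, that is, end of supply + 90 − date of first record. Confirmation is lost if the gap exceeds R. Since the gap cannot exceed 182.6 days, loss through discontinuation needs R < 182.6. This covers first records in the last 182.6 − 90 = 92.6 days of supply or in the grace period, about the last 183 days of follow-up. Earlier first records are safe from this mechanism.

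**Step 2: share lost at a given R.** For a uniform gap the share is 1 − R/182.6. For an exponential gap with mean m, truncated at 182.6 days, it is [exp(−R/m) − exp(−182.6/m)] / [1 − exp(−182.6/m)].

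| First record | R (days) | Uniform | m = 30 | m = 60 | m = 90 |
|---|---|---|---|---|---|
| 30 days before supply ends | 120 | 34.3% | 1.6% | 9.2% | 15.2% |
| Last day of supply | 90 | 50.7% | 4.8% | 18.4% | 27.2% |
| 45 days into grace | 45 | 75.4% | 22.1% | 44.6% | 54.7% |

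**Step 3: first records spread evenly over a fixed supply S plus 90 days.** For a uniform gap the average is 182.6 / [2(S + 90)]; with S = 180 this is 182.6/540 = 33.8%. Across the four gap models the loss is 16–51% for S = 90, 11–34% for S = 180, 6.5–20% for S = 365 and 3.6–11% for S = 730.

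**Step 4: simulation with variable persistence.** Assumptions: first records at 3% per year; exponential discontinuation; gap truncated at 180 days with an untruncated median of 30–120 days; a first record multiplies the stopping rate by 1 to 4; follow-up capped at five years. Share of confirmable on-treatment cases lost:

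| Median persistence | Loss |
|---|---|
| 120 days | 15–36% |
| 180 days | 12–29% |
| 365 days | 7–18% |

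If the standard error of the log hazard ratio scales as 1/√events, a 7% loss multiplies it by 1/√0.93 = 1.04 and a 36% loss by 1/√0.64 = 1.25.

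**Step 5: crude rates.** Over these cells the crude rate is about 1.9–2.8% per year against a first-record rate of 3.0%. When a first record does not speed stopping, the rate is 1.0–1.8% in days 0–90, 2.4–2.9% in days 90–180, and 3.0% after day 180. All of that shortfall is therefore a start-up lag: no one enters with a dementia diagnosis, so confirmed cases take time to accrue. Fourfold faster stopping lowers the crude rate further, at 120 days' persistence from 2.55% to about 2.5% (gap median 30 days) or from 2.15% to about 1.9% (gap median 120 days). With a true hazard ratio of 1, no faster stopping, a gap median of 120 days and median persistence of 120 v 365 days, the arms show about 2.2% v 2.6% per year, a crude ratio of 2.2/2.6 = 0.85.

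**Step 6: hazard ratio.** True value 1, median persistence 120 v 365 days, rate ratio stratified in 15-day bands of follow-up:

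| Effect of first record on stopping | Dated to second record | Dated to first record |
|---|---|---|
| None | 1.00–1.01 | about 1.0 |
| 2–4 times faster | 0.93–0.99 | about 1.0 |

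**The case against.** An event dated after censoring is ordinary right-censoring. The plan defines the outcome as existing at the second record, and dating it there avoids using future information. That is a legitimate explicit choice, and this part of the objection stands.

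The planned estimate is a cause-specific hazard ratio, which compares patients at the same follow-up time. A reader might infer that it must be biased because one arm may stop sooner. The documents do not support that: unequal persistence alone leaves it at about 1. The bias needs faster stopping after a first record as well, and the documents give data on neither condition.

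A reader might also put the whole fall in the crude rate down to the mismatch between 90 days and 6 months. Step 5 shows that most of it is the start-up lag, which is the same in both arms at a given follow-up time.

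Analysis 2 already drops censoring at discontinuation. However, it uses the claims-only outcome, so it does not test the analysis 4 definition. A different grace period may be intended for analysis 4, since the 90 days is tied to the main analyses and the diagrams are not available, but none is stated.

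None of this answers the lost events or the dependence of the crude rates on persistence.

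**Conclusion.** The point holds for analysis 4 as a loss of events and of interpretability. It does not show that the hazard ratio is biased. As written, a first record in about the last 183 days of follow-up can go uncounted. The loss is 7–36% under the simulation's assumptions; the fixed-supply calculation gives 3.6–51% over a wider set. All these figures rest on assumed gaps and persistence. Crude arm-specific rates will vary with persistence even under the null. The hazard ratio moves to about 0.93–0.99 only when first records speed stopping 2–4 fold and median persistence is 120 v 365 days; otherwise it is unbiased. Any difference between analysis 4 and analysis 1 may therefore partly reflect persistence as well as outcome definition.

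A reader might extend this to analyses 1 and 3, which share the follow-up rule. The text does not support that: it states neither a window nor a dating rule for the two outpatient claims, and one inpatient claim is enough alone. Nor does the evidence justify replacing the plan's dating rule, which would exchange one debatable choice for another.

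**What to change.** Keep dating to the second record as stated. Add to section 6c a prespecified parallel version of analysis 4 in which:

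- the first record, claim or prescription, falls after the index date and within follow-up (the after-index condition matters because entry excludes prior dementia diagnoses but not prior symptomatic prescriptions);
- the confirming record is sought for the full 6 months regardless of index-drug status, while the patient is alive and enrolled;
- the event is dated to the first record.

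Report incidence rates and hazard ratios from both versions, and state that the main version does not seek confirmation after censoring.

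The cost is a few sentences, a small programming change on claims already held, and one further run. The downside is that the parallel version uses claims after discontinuation, though for confirmation only. Patients who die or disenrol within the 6 months still cannot be confirmed, nor can those whose 6 months run past the end of the data.

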Data Analysis for Drug Repurposing for Effective Alzheimer's Medicines – Pentoxifylline vs Cilostazol

NCT05635370

July 7, 2023

1. Comparison Details

a. Intended aim(s)

To evaluate the comparative risk of dementia onset between patients treated with Pentoxifylline versus cilostazol for peripheral artery disease (PAD).

b. Primary endpoint

Incident dementia (i.e., Alzheimer's disease, vascular dementia, senile, presenile, or unspecified dementia, or dementia in other diseases classified elsewhere).

2. Person responsible for implementation

[name]

3. Data Source(s)

Medicare, 2008-2018

4. Study Design Diagrams

[figure not shown]
[figure not shown]

Figure- Alternate analysis approaches

[figure not shown]
■■■ Included person-time
 ■■■ Excluded person-time

Provides 'on treatment' estimates for the outcome risk and addresses exposure person-time misclassification

Analysis 1

[figure not shown]

Analysis 3

[figure not shown]

Addresses reverse causation due to preferential treatment initiation related to unrecorded cognitive impairment at study start and informative-censoring

Analysis 2

Analysis 4

5. Cohort Identification

a. Cohort Summary

This study will employ a new user, active comparator, observational cohort study design comparing Pentoxifylline versus Cilostazol. The patients will be required to have continuous enrollment during the baseline period of 365 days before initiation of study drugs (cohort entry/index date). Follow-up for the outcome (dementia) differs between analyses. Follow-up begins the day after drug initiation (analysis 1, 3, 4); 180 days after drug initiation (analysis 2).

b. Key details regarding cohort creation

Index date:

- Day of initiation of new Pentoxifylline versus Cilostazol use

Inclusion criteria for analyses 1, 3, 4:

- Aged \geq 65 years on the index date
- 365 days enrollment in Medicare Parts A, B, and D with no HMO coverage prior to index date
- No use of Pentoxifylline versus Cilostazol, any time prior to index date (all available lookback approach with a minimum of 365 days)
- No diagnosis of dementia any time prior to and including index date
- No history of nursing home admission recorded in any time prior to and including index date
- At least two claims with peripheral artery disease diagnosis recorded in 365 days prior to index date (ICD-9 or ICD-10 codes)¹

Inclusion criteria for analysis 2:

- Aged \geq 65 years on the index date

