- 365 days enrollment in Medicare Parts A, B, and D with no HMO coverage prior to index date
- No use of Pentoxifylline versus Cilostazol, any time prior to index date (all available lookback approach with a minimum of 365 days)
- No diagnosis of dementia any time prior to and including index date
- No history of nursing home admission recorded in any time prior to and including index date
- At least two claims with peripheral artery disease diagnosis recorded in 365 days prior to index date (ICD-9 or ICD-10 codes)¹

- 180-day continuous use of Pentoxifylline versus Cilostazol starting on the index date

c. Flowchart of the study cohort assembly

	Less Excluded Patients	Remaining Patients
All patients		23,466,175
Did not meet cohort entry criteria	-23,393,311	72,864
Excluded due to insufficient enrollment	-45,683	27,181
Excluded based on Dementia Exclusion	-6,100	21,081
Excluded based on Nursing Home Admission	-4,080	17,001
Excluded based on Peripheral artery disease Diagnosis	-4,524	12,477
Excluded anyone aged <65 at index	-2,079	10,398
Patients in Pentoxifylline group		1,701
Patients in Cilostazol group		8,697
Final cohort		10,398

6. Variables

a. Exposure-related variables:

Study drug:

The study exposure of interest is initiation of Pentoxifylline

Comparator:

Cilostazol

b. Covariates:

Demographics	
Age	Region
Gender	Calendar year of index date
Race	Low income subsidy

Dementia risk factors	
Diabetes	Depression
Obesity	Anxiety
Hypertension	Bipolar disorder
Coronary artery disease	Schizophrenia

Markers for healthy behavior, frailty, healthcare use	
Smoking	Number of hospitalizations
Mammography	Number of physician office visits
Colonoscopy	Number of serum creatinine tests ordered
Fecal occult blood test	Composite frailty score
Influenza vaccination	Number of C-reactive protein tests ordered
Pneumococcal vaccination	Osteoporosis
Herpes zoster vaccination	Fractures
Bone mineral density test	Falls
Number of distinct generic agents	Use of supplemental oxygen
Number of emergency room visits	Combined comorbidity score
Number of outpatient visits	

Comedication use	
Lithium	Diuretics
Anti-epileptic mood stabilizers	Nitrates
Anti-epileptics (other than mood stabilizers)	Lipid lowering drugs

Atypical antipsychotics	Non-insulin diabetes medications
Benzodiazepines	Insulin
Serotonin-norepinephrine reuptake Inhibitors	Antidepressants
Selective serotonin reuptake inhibitors	Angiotensin II receptor blockers (ARBs)

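### For analyses 1, 3 and 4, the section 6c text does not end follow-up when a patient first fills the other study drug, so some comparator time can count in the index arm

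*Combined protocol and SAP*

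**What the plan says.** Section 6c states that for analyses 1, 3 and 4 "the follow-up will start the day after initiation of Pentoxifylline and Cilostazol and will continue until the earliest date of the following events". Five events follow: the outcome, end of registration, end of the study period, death, and discontinuation of the index drug. Discontinuation is dated at "the last continuous treatment episode of the index drug (Pentoxifylline and Cilostazol) plus a defined grace period", specified as "90 days after the end of the last prescription's days' supply in main analyses".

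The other study drug is addressed only before cohort entry, through the new-user criterion in section 5b: "No use of Pentoxifylline versus Cilostazol, any time prior to index date". The visible text has no rule for switching or adding on after the index date.

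A caption in section 4 describes on-treatment "estimates for the outcome risk and addresses exposure person-time misclassification". It stands directly above the label for analysis 1. The diagrams carry a legend that separates "Included person-time" from excluded person-time, but they are not shown. Section 9 estimates a hazard ratio averaged over all follow-up, and hazard ratios for intervals.

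**The concern.** The study compares two drugs head to head. A grace period allows for irregular refilling or a lingering effect. Neither reason plainly covers time after a claim shows that the other study drug was dispensed. Under the 6c text, that time stays in the arm the patient entered, and it enters the section 9 hazard ratio.

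Three consequences are possible:

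- If effects are immediate and switching is unrelated to dementia risk, the hazard ratio moves toward 1.
- If the index drug's effect lasts as long as the counted tail, the tail causes no bias.
- If switchers differ in dementia risk, the bias can go either way.

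**Working it through.** **What comes from the documents.** The 90-day grace period and the five stop events (section 6c). The documents give no switch rate, time on drug, event count or power calculation, so there is no plan figure to reproduce.

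**Days counted after a switch.** If the other drug starts r days after index supply ends, the days still counted in the index arm are max(0, 90 − r), unless another listed event comes first. That is 90 days for r = 0, 60 for r = 30, and none for r of 90 or more. A patient who adds the other drug while still filling the index drug is counted for the whole overlap as well.

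**Assumed inputs.** 5–20% of patients switch; r = 0–60 days; mean follow-up 200–365 days (midpoint 282.5).

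**Formulas.** The affected share of person-time is f = switch share × (90 − r) / mean follow-up. With immediate effects, equal shares in both arms and non-prognostic switching, observed HR = ((1 − f)·HR + f) / ((1 − f) + f·HR). The true HR is set at 0.80.

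| Case | f | Observed HR |
|---|---|---|
| Low | 0.05 × 30 / 365 = 0.4% | 0.801 |
| Midpoint | 0.10 × 60 / 282.5 = 2.1% | 0.8042 / 0.9958 = 0.808 |
| All extremes together | 0.20 × 90 / 200 = 9.0% | 0.818 / 0.982 = 0.833 |

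**Against sampling error.** SE(log HR) = 2/√D. For an assumed D of 50 to 200 events this is 0.283 to 0.141. The midpoint log shift is ln(0.8077/0.80) = 0.0096, or 3–7% of one SE. The extreme shift is 0.0404, or 14–29%.

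**If the effect persists for L days after index supply ends or the switch occurs.** Misattributed days become max(0, 90 − r − L).

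- Midpoint: L = 30 gives f = 0.10 × 30 / 282.5 = 1.1% and HR 0.804; L = 60 gives 0.800.
- Extreme: L = 30 gives f = 6.0% and HR 0.822; L = 60 gives 3.0% and 0.811; L = 90 gives 0.800.

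**Add-on overlap (separate from the table).** Suppose a share g of cilostazol-arm time is on both drugs and only pentoxifylline has an effect. Then observed HR = 0.80 / ((1 − g) + 0.80g): 0.802 at g = 1% and 0.808 at g = 5%.

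**Prognostic switching.** Suppose 3% of one arm's time carries twice the baseline hazard.

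- Cilostazol arm only: 0.80 / (0.97 + 0.03 × 2 × 0.80) = 0.786.
- Pentoxifylline arm only: 0.97 × 0.80 + 0.03 × 2 = 0.836.

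**Cost of censoring at the switch.** If events are proportional to time, the SE widens by 1/√(1 − f) − 1: 1.1% at the midpoint and 4.8% at the extreme. Variance rises by 1/(1 − f) − 1: 2.2% and 9.9%. The squared bias removed, as a share of SE² at 50 to 200 events, is 0.1–0.5% at the midpoint and 2.0–8.2% at the extreme.

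**The case against.** The strongest reply is that the visible text is not the full person-time specification. Analyses 1 and 3 have the same inclusion criteria, outcome definition and stop list, so whatever separates them must lie in material not visible here, most likely the section 4 diagrams. A reader might infer that the plan has no switch rule at all. The documents do not support that; they show only that 6c states none. For the same reason, the on-treatment aim cannot be tied with certainty to all three analyses.

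The second reply is that a 90-day grace period deliberately assigns time after supply ends to the index drug, and that a lasting effect makes this correct. This stands as a reason to keep the grace period for patients who do not start the other drug, and to keep the present rule as a sensitivity analysis. The reference to main analyses also suggests other grace periods elsewhere; a shorter one would shrink the tail.

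The third reply is that the change does not reduce mean squared error. This also stands: on the assumptions used here, the added variance exceeds the squared bias in both the midpoint and the extreme case. The gain is a contrast that means what it is labelled to mean.

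The fourth reply is that censoring at a switch may itself be informative, a problem that another section 4 caption names. This stands too. The figures of 0.786 and 0.836 show that the direction of bias is open; they do not show that the change would remove it.

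**Conclusion.** The point holds for the 6c text. Followed literally, it counts up to 90 days after index supply ends, plus any add-on overlap, in the index arm even when the patient is on the comparator. Severity is minor to moderate. The size is unknown and probably small: a shift of about one-hundredth in a hazard ratio of 0.80 at the midpoint, and about three-hundredths with every assumed extreme combined. These are illustrations that leave out add-on overlap. They are not bounds, and they rest on assumed switch rates, timing, follow-up and event counts.

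Two stronger readings should be avoided. One is that the index drug in 6c means either drug, so that follow-up would run on through the second; the natural reading is the drug the patient started. The other is that the omission must pull the result toward 1, which requires immediate effects and non-prognostic switching, and the documents establish neither.

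**What to change.** 1. Check 6c against the section 4 diagrams. If they already end counted time at a switch, state that rule in 6c so that the two agree.
2. If they do not, add to the 6c list for analyses 1, 3 and 4: *date of first dispensing of the other study drug (switch or add-on)*. Keep the 90-day grace period for patients who do not start the other drug.
3. Report by arm the number of switchers and add-on users, the days from end of index supply to first fill of the other drug, and the person-time affected.
4. Keep the present rule as a sensitivity analysis. Comparing the two rules shows how far the result depends on the choice. It does not separate misclassification removed from informative censoring added, so the change should not be presented as removing bias from prognostic switching.
5. Do not use analysis 2 to show how much this matters. It requires "180-day continuous use of Pentoxifylline versus Cilostazol starting on the index date", starts follow-up at day 180 and caps it at 1095 days, so it differs in more than the handling of switches.

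The cost is one line in 6c, one table and a re-run on dispensing claims that the discontinuation rule already needs. Precision falls slightly, as shown in the working, and some possibly informative censoring is added to a rule that already censors at discontinuation.

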For analysis 2, the follow-up will start 180 days after initiation of Pentoxifylline and Cilostazol and will continue until the earliest date of the following events:

- The first occurrence of the outcome of interest, unless otherwise specified for selected outcomes,
- The date of end of continuous registration in the database,
- End of the study period,
- Measured death event occurs,
- Maximum allowed follow-up time (1095 days) reached

7. Propensity score analysis

We will use a propensity-score (PS)²-based approach to account for measured confounding in this study. The PS will be calculated as the predicted probability of initiating the exposure of interest (i.e., the repurposing candidate) versus the reference drug conditional on baseline covariates using multivariable logistic regression constructed separately in each data source. On average, patients with similar PSs have similar distribution of potential confounders used to estimate the PS. Therefore, analyses conditioned on the PS provide effect estimates that are free from measured confounding. For all our analyses, initiators of each exposure of interest will be matched with initiators of the reference exposure based on their PS within each data source.³ Pair matching will be conducted using a nearest-neighbor algorithm, which seeks to minimize the distance between propensity scores in each pair of treated and reference patients,⁴ and a caliper of 0.025 on the natural scale of the PS will be used to ensure similarity between the matched patients.⁵

We report multiple diagnostics for PS analysis in this protocol. First, the PS distributional overlap is provided between two groups before and after matching to ensure comparability of these groups.⁶ Next, balance in each individual covariate between two treatment groups is reported using standardized differences.⁷

8. Table for covariate balance

Variable	Crude			PS-Matched		
	Pentoxifylline (N = 1,701)	Cilostazol (N = 8,697)	St. Diff	Pentoxifylline (N = 1,687)	Cilostazol (N = 1,687)	St. Diff
Demographics						
Age, mean (SD)	76.2 (7.3)	75.3 (6.9)	0.13	76.2 (7.2)	76.3 (7.2)	-0.01
Gender, n (%)						
Male	828 (48.7)	4733 (54.4)	-0.12	822 (48.7)	827 (49)	-0.01
Female	873 (51.3)	3964 (45.6)	0.12	865 (51.3)	860 (51)	0.01
Race, n (%)						
White	1386 (81.5)	7096 (81.6)	0.00	1377 (81.6)	1347 (79.8)	0.05
Black	156 (9.2)	935 (10.8)	-0.05	156 (9.2)	176 (10.4)	-0.04
Hispanic	70 (4.1)	237 (2.7)	0.08	67 (4)	65 (3.9)	0.01

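### Analysis 2 starts follow-up at day 180 but excludes dementia only through the index date, so patients with a dementia claim in between stay eligible and, on some readings, count as incident

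*Combined protocol and SAP*

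**What the plan says.** Section 5a gives the start of follow-up: "Follow-up begins the day after drug initiation (analysis 1, 3, 4); 180 days after drug initiation (analysis 2"). Section 6c repeats it for analysis 2: "For analysis 2, the follow-up will start 180 days after initiation of Pentoxifylline and Cilostazol".

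Section 5b gives analysis 2 its own inclusion list. Its dementia criterion is the one used for the other analyses: "No diagnosis of dementia any time prior to and including index date". The only added criterion is "180-day continuous use of Pentoxifylline versus Cilostazol starting on the index date".

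Section 6c defines the outcome for analyses 1 to 3 as one inpatient "claim or 2 outpatient claims in analysis 1, 2, 3", with no rule for dating the event. Analysis 4, which uses a different outcome definition, does have one: the two items must fall "within 6 months of each other with outcome date assigned to second event in the sequence".

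For analysis 2, follow-up ends among other events at "The first occurrence of the outcome of interest, unless otherwise specified for selected outcomes". The closing qualifier is absent from the matching line for analyses 1, 3 and 4, and nothing readable elsewhere specifies an exception.

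**The concern.** In analyses 1, 3 and 4 the dementia exclusion runs through the index date and follow-up starts the next day, so eligibility and time zero meet. In analysis 2 they separate by 180 days. The continuous-use requirement was carried forward to day 180; the dementia-free requirement was not.

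A caption in section 4 names reverse causation from cognitive impairment not yet recorded at study start. The figure is not readable, so linking that caption to analysis 2 is an inference from the layout, but a 180-day lag fits that purpose. Dementia claims soon after initiation are the ones most likely to reflect impairment already present at initiation. If patients with such claims enter follow-up and are then counted as new cases, the lag lets back in part of what it was apparently meant to remove. The exposure would be greatest in the first of the "interval specific hazard ratios (1, 2, and 3 years") planned in section 9.

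**Working it through.** **Step 1: the rules side by side.**

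| | Dementia excluded through | Follow-up starts | Gap |
|---|---|---|---|
| Analyses 1, 3, 4 | index date | day after initiation | none |
| Analysis 2 | index date | day 180 | days 1 to 180 |

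No readable text excludes or censors a patient for a dementia claim in the gap. The flowchart in section 5c has a single dementia step (6,100 removed) and no step for analysis 2. Its arithmetic is sound: 23,466,175 − 23,393,311 − 45,683 − 6,100 − 4,080 − 4,524 − 2,079 = 10,398 = 1,701 + 8,697.

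**Step 2: what happens to a patient with a claim in the gap.**

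- *Reading (a), first ever.* A patient who met the outcome before day 180 contributes no event. A patient with one outpatient claim before day 180 and one after is not an event in follow-up if the date is the earlier of the two, and is one if the date is the later.
- *Reading (b), first after day 180.* Patients who fully met the outcome earlier can also be counted when dementia is coded again.

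**Step 3: illustrative size.** The documents give no dementia rate, no gap between claims and no analysis 2 sample size, so every input here is an assumption: constant hazard h of a first dementia claim of 0.015, 0.030 or 0.045 per year, no competing death, and time L counted from day 180 (365.25 or 1,095 days; the plan does not state the origin of the 1,095 days). Let S(d) = exp(−h·d/365.25).

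Reading (b), with f the fraction of gap cases carried over:

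- pre = 1 − S(180) = 7.4, 14.7 and 21.9 per 1,000 patients at the three rates.
- post = S(180) − S(180 + L). At h = 0.030 this is 29.1 per 1,000 in year 1 and 84.8 per 1,000 over 1,095 days.
- share = f·pre / (f·pre + post). At h = 0.030 and f = 1: 14.7/(14.7 + 29.1) = 33.5% in year 1, and 14.7/(14.7 + 84.8) = 14.8% over 1,095 days.

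| f | Year 1 | 1,095 days |
|---|---|---|
| 0 | 0% | 0% |
| 0.25 | 11% | 4% |
| 0.5 | 20% | 8% |
| 1 | 33–34% | 14–15% |

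Reading (a) with the event dated to the second claim, a fixed gap of g days between claims, a fraction q of cases found by outpatient pairs, and every first outpatient claim followed by a second:

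- A = S(180 − g) − S(180), the straddling pairs.
- B = S(180) − S(180 + L − g), pairs wholly after day 180.
- C = S(180) − S(180 + L), the remaining cases.
- share = q·A / [q(A + B) + (1 − q)C].

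Example at h = 0.030, year 1, q = 1, g = 90: A = 7.31 and B = 22.03 per 1,000, so 7.31/29.34 = 24.9%.

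| q | g (days) | Year 1 | 1,095 days |
|---|---|---|---|
| 0.5 | 30 / 60 / 90 | 4.2 / 8.3 / 12.5% | 1.4 / 2.9 / 4.3% |
| 1 | 30 / 60 / 90 | 8.3 / 16.6 / 24.9% | 2.9 / 5.7 / 8.6% |

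The table is for h = 0.030; the other two rates change these entries by less than 0.2 percentage points. Reading (a) with the event dated to the earlier of the two claims gives 0% throughout.

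**Step 4: does a share of events translate into bias?** Under reading (b), take h = 0.030, no true effect after day 180, and a hazard ratio k between arms in the gap only. The exposed-arm risk is f(1 − e^(−kht)) + e^(−kht)(1 − e^(−hL/365.25)), with t = 180/365.25, and the comparator has k = 1. For f = 0.25, 0.5 and 1:

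| k | Risk ratio, year 1 | Risk ratio, 1,095 days |
|---|---|---|
| 0.5 | 0.95 / 0.91 / 0.84 | 0.99 / 0.97 / 0.93 |
| 1 | 1.00 | 1.00 |
| 1.5 | 1.05 / 1.09 / 1.16 | 1.01 / 1.03 / 1.07 |

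The shift can go either way, and it is nil when the arms do not differ in the gap.

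**The case against.** The endpoint is labelled incident dementia, so first ever is the more natural reading. On that reading a patient who met the outcome before day 180 has already reached the end of follow-up and adds neither event nor person-time. This stands, and it limits what can be claimed. A reader might infer that the lag is weakened however the rule is read; it is not, because first ever with first-claim dating leaves the counted events unaffected. A reader might also take the share of about one third as the expected size. That figure needs the less natural reading and also needs every early case to survive, stay enrolled and qualify again.

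One outpatient claim alone does not meet the analysis 2 outcome, so a pair completed after day 180 is arguably incident by the plan's own definition. That is fair as far as the outcome goes, but the baseline criterion bars any diagnosis, which is stricter. The plan also leaves the event date open, so it does not settle whether such pairs count.

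The diagrams are not readable and may show an exclusion window through day 180. If they do, the problem is a mismatch between text and figure, and the written criterion must be matched to the figure.

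Excluding only patients who fully met the outcome by day 180, with a dating rule, is a legitimate alternative. It keeps patients with one unconfirmed claim, but it applies a looser standard at time zero than the plan applies at the index date.

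**Conclusion.** The concern holds in a limited form. The analysis 2 exclusion is misaligned with its time zero: a patient with a dementia claim on days 1 to 180 meets every written criterion. Whether any such patient is counted as incident depends on two things that the plan leaves open, the meaning of first occurrence and the date of a two-claim outcome.

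The size is unknown and can be zero. With assumed rates of 15 to 45 per 1,000 person-years, gap cases number about 7 to 22 per 1,000 patients. Straddling pairs dated to the second claim make up about 4–25% of year-1 events and 1–9% over 1,095 days. Under reading (b) the shares run from 0% to 33–34% and from 0% to 14–15%.

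A reader might infer that the analysis 2 hazard ratio is biased in a known direction. The documents do not support that, since they give nothing on how gap claims differ between arms. Analyses 1, 3 and 4 are not affected. This should be fixed because the correction is cheap and removes the ambiguity; confidence is moderate, given the missing diagrams.

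**What to change.** For analysis 2 only:

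1. Change the inclusion criterion to require no dementia diagnosis, on any single claim, from the start of available data through day 180 after the index date. This keeps the standard already used at baseline. Continuous use to day 180 is already required, so the change uses no information from after time zero.
2. Build the analysis 2 cohort on that criterion.
3. State that all claims defining the outcome must fall after day 180, and which claim sets the outcome date.
4. Say what first occurrence means, and either specify or delete the qualifier about selected outcomes. Once step 1 is in place, first ever and first after day 180 coincide.
5. Check the design diagrams and make text and figure agree.

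The cost is one changed criterion and a few sentences. The downside is a slightly smaller analysis 2 cohort, including the loss of some patients whose single claim in the gap would never have been confirmed.
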